9.2.1. Serious Adverse Events

Study site personnel must alert the sponsor or its designee of any SAE **within 24 hours** of investigator awareness of the event via a sponsor-approved method. Serious adverse event reporting to the sponsor begins after the patient has signed Informed Consent.

If alerts are issued via telephone, they are to be immediately followed with official notification on study-specific SAE forms. This 24-hour notification requirement refers to the initial SAE information and all follow-up SAE information. Patients with a serious hepatic AE should have additional data collected using the EDC (Section 9.4.5.1).

An SAE is any AE from this study that results in 1 of the following outcomes:

- death
- initial or prolonged inpatient hospitalization
- a life-threatening experience (that is, immediate risk of dying)
- persistent or significant disability/incapacity
- congenital anomaly/birth defect
- Important medical events that may not be immediately life threatening or result in death or hospitalization but may jeopardize the patient or may require intervention to prevent one of the other outcomes listed in the definition above. Examples of such medical events include allergic bronchospasm requiring intensive treatment in an emergency room or at home, blood dyscrasias or convulsions that do not result in inpatient hospitalization, or the development of drug dependency or drug abuse.

Previously planned (prior to the signing of ICF) surgeries should not be reported as SAEs unless the underlying medical condition has worsened during the course of the study.

The following terms will be utilized to assess the relationship of the SAE to administration of study treatment:

- **Probably related:** a direct cause and effect relationship between the study treatment and the AE is likely.
- **Possibly related:** a cause and effect relationship between the study treatment and the AE has not been demonstrated at this time and is not probably, but is also not impossible.
- **Unlikely:** likely to be due to another etiology.
- **Not related:** without question, the AE is definitely not associated with study drug.

Although all AEs are recorded in the case report form or EDC after signing informed consent, SAE reporting to the Sponsor begins after the subject has signed informed consent and has received the study drug. However, if an SAE occurs after signing informed consent, but prior to receiving the study drug, AND is considered Reasonably Possibly Related to a study procedure then it MUST be reported.

Investigators are not obligated to actively seek AEs or SAEs in patients once they have discontinued and/or completed the study. Serious adverse events occurring after a patient has taken the last dose of study drug will be collected for 30 days after the last dose of the study drug. However, if the investigator learns of any SAE, including a death, at any time after a patient has been discharged from the study, and he/she considers the event reasonably possibly related to the study treatment or study participation, the investigator must promptly notify the sponsor and/or its designee.

Pregnancy (during maternal or paternal exposure to study treatment) does not meet the definition of an AE. However, to fulfill regulatory requirements any pregnancy should be reported following the SAE process to collect data on the outcome for both mother and fetus.

The designated medical monitor of the sponsor will monitor safety data throughout the course of the study. The sponsor and/or its designee will review SAEs within appropriate timeframes to meet reporting obligations imposed by regulatory authorities. All serious and unexpected AEs for this study will be reported to regulatory authorities in accordance with local laws, directives, and regulations.

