- ^c Serum pregnancy test at Screening and urine pregnancy test at subsequent visits.
- ^d If the result of the QuantiFERON®-TB Gold test is positive, the patient will be excluded from the study. If result is indeterminate, a single re-test will be allowed. If the result of the second test is positive or still indeterminate, the patient will be excluded from the study. Patients who have been vaccinated with BCG at any time in the past do NOT need to undergo testing. Documentation of previous vaccination is required.
- ^e On days when there is pre-dose PK sampling (at 1 week, 2 weeks, 4 weeks, 8 weeks and 12 weeks after the first dose), the dosing will be at the site after pre-dose sampling (patients will be instructed to not dose at home). The patients will be required to bring to the CRU their study treatment kit with all unused tablets. On all other days, patients should take their medication at approximately the same time in the morning. It is recommended (but not required) that the dose should be taken with food.
- ^f A full physical examination will be conducted at screening and on Week 4. Physical examination must include evaluation of the skin and mucus membranes. A physical examination may be performed at other visits at the investigator's discretion.
- ^g Height at screening visit only.
- ^h Single BP readings and other vital signs (in a seated position) on Day 1 and subsequent visits.
- ⁱ Single 12-lead ECG readings (in supine position, for at least 5 minutes prior to the ECG reading). The screening ECG may be repeated at the investigator's discretion. When scheduled at the same time, the following order of procedures is recommended: ECGs, vital signs, and blood collection (and/or other study procedures).
- ^j Clinical laboratory tests will include hematology, serum chemistry, and urinalysis.
- ^k Pre-dose samples are to be obtained at 1 week, 2 weeks, 4 weeks and 8 weeks weeks after the first dose of study drug. On the last day of dosing (Day 85/Week 12), the following samples are to be collected: pre-dose and 1, 2, 4, 8 hr post last dose. One sample will also be collected on weeks 2, 4, 6 and 8 weeks post last dose. One sample should be taken at the early termination visit, if applicable. Timing of PK sample collection may be adjusted based on clinical needs. Actual sampling dates and times must be accurately recorded.

3. Introduction

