5.1. Overall Design

This is a multicenter, randomized, double-blind, placebo-controlled, parallel design Phase 2a study in patients with moderate to severe chronic plaque psoriasis.

Screening (up to 28 days prior to first dose of study drug) allows for evaluation of inclusion and exclusion criteria. Following Screening, all eligible patients will be randomly assigned (in 1:1:1 ratio) to PRCL-02 Dose 1, PRCL-02 Dose 2, or placebo and will receive study drug for 12 weeks. Following completion of 12-week treatment, all patients will attend Follow-Up Visits at 2, 4, 6 and 8 weeks after the last dose of study drug.

Efficacy and safety assessments will be performed as defined in the Schedule of Activities (Section 2).

Figure PRCL 1 illustrates the study design.

Study governance considerations are described in detail in [Appendix 3](#).

[figure not shown]

Figure PRCL 1

Illustration of study design for Clinical Protocol PRCL-PoC

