10.3.4. Safety Analyses

The safety analysis will be conducted using the safety population.

The safety and tolerability of treatment will be assessed by evaluating the following:

- Treatment-emergent AEs (TEAEs) by Preferred Term and maximum severity
- SAEs
- AEs leading to discontinuation
- Vital signs
- ECGs
- Laboratory measurements
- Physical examination

Treatment-emergent adverse events are defined as the reported AEs that first occurred or worsened during the double-blind treatment phase and follow-up compared with baseline. The most recent version of Medical Dictionary for Regulatory Activities Preferred Term will be used. Treatment-emergent adverse events will be summarized by the number and percentage of patients with the event.

Other safety parameters that will be assessed include physical examinations, safety clinical laboratory parameters, vital signs, and ECG parameters. The parameters will be listed and summarized using standard descriptive statistics. Additional analysis will be performed if warranted upon review of the data.

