9. SCHEDULE OF ASSESSMENTS

Procedure	Screening									FU	EoS
Visit #	1	2	3	4	5	6	7	8	9	10	11
Study Days	-28 to -1	1	8	15	29	57	85	99	113	127	141
Window Period (Days)		±2	±2	±2	±2	±2	±2	±2	±2	±2	±2
Week	-	-	1	2	4	8	12	14	16	18	20
Informed consent	X										
Demographics	X										
Medical history	X										
Inclusion and exclusion criteria	X	X									
Pregnancy test (♀)	X	X	X	X	X	X	X	X	X	X	
Serum FSH (PMP ♀)	X										
QuantiFERON TB Test		X									
HIV/hepatitis screen	X										
Randomization		X									
Study drug dispensing		X	X	X	X	X					
Study drug accountability			X	X	X	X	X				X if ET
Safety Evaluations											
Physical examination	X	X	X	X	X	X	X				X
Height/weight	X	X	X	X	X	X	X				X
Vital signs (pulse and BP)	X	X	X	X	X	X	X	X	X	X	X
12-lead ECG	X	X	X	X	X	X	X				X
Clinical laboratory tests	X	X	X	X	X	X	X				X
AE monitoring	X	X	X	X	X	X	X	X	X	X	X
Concomitant medications	X	X	X	X	X	X	X	X	X	X	X
Efficacy and Other Evaluations											
PASI	X	X	X	X	X	X	X	X	X	X	X
sPGA	X	X	X	X	X	X	X	X	X	X	X
PK sampling			X	X	X	X	X	X	X	X	X
Plasma sample collection for PGx assessments		X									

See protocol for footnotes.

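### The 30-day limit on SAE collection after the last dose ends 26 days before follow-up and the TEAE period do, and conflicts with other safety instructions in the protocol

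*Protocol*

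**What the plan says.** **End of SAE collection.** Protocol 9.2.1 states that SAEs arising once the patient has stopped study drug "will be collected for 30 days after the last dose of the study drug". The same paragraph adds a duty to notify the sponsor of later SAEs. It applies once the patient has been discharged from the study, and only to events that the investigator learns of and considers reasonably possibly related to treatment or participation.

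**Length of follow-up.** Protocol 5.1 states that "all patients will attend Follow-Up Visits at 2, 4, 6 and 8 weeks after the last dose of study drug". The schedules in Protocol Section 2 and SAP Section 9 mark AE monitoring at every visit through the end-of-study (EoS) visit on Day 141.

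**Analysis period.** Protocol 10.3.4 counts as treatment-emergent those AEs that "first occurred or worsened during the double-blind treatment phase and follow-up compared with baseline". SAP 6.2 counts AEs from the first dose and gives no end date. It tabulates treatment-emergent SAEs by system organ class and preferred term, again with no 30-day limit, and has a separate table of common non-serious TEAEs. TEAEs are the secondary safety endpoint.

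**Instructions that point the other way.** Protocol 9.2.1 also requires sites to alert the sponsor within 24 hours of learning of any SAE, and says that all AEs are recorded from consent onwards.

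**Start of SAE reporting.** One sentence of 9.2.1 reads "Serious adverse event reporting to the sponsor begins after the patient has signed Informed Consent". A later one reads "SAE reporting to the Sponsor begins after the subject has signed informed consent and has received the study drug", with an exception for pre-dose SAEs related to a study procedure.

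**The concern.** The 30-day clock runs from the last dose, not from study exit. A completer is therefore still under observation, with two visits to come, when the stated SAE window closes. The post-discharge duty does not bridge the interval, because that patient has not been discharged. If it were stretched to cover the interval, late SAEs would pass through a causality filter that does not apply to non-serious AEs over the same days.

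At stake is the consistency of the safety tables. A site that follows the 30-day sentence may send no SAE form for an event on Day 120, while a site that follows the any-SAE instruction would send one. The treatment-emergent SAE table and the non-serious TEAE table could then cover different lengths of follow-up without saying so. The SAP cannot repair this: SAP 1.1 lets it supersede only the statistical sections of the protocol, and the rule sits in Section 9.2.1.

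**Working it through.** **Inputs**
- Last day of dosing for a completer: Day 85 (Protocol Section 2, PK sampling footnote).
- Follow-up visits: 2, 4, 6 and 8 weeks after the last dose (Protocol 5.1).
- EoS: Day 141, with a ±2-day window on visits (Protocol Section 2; SAP Section 9).
- SAE collection: 30 days after the last dose (Protocol 9.2.1).
- Screening: Days -28 to -1 (both schedules).

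**Reproducing the schedule**
- Twelve weeks from Day 1: 1 + 84 = Day 85.
- Follow-up visits: 85 + 14, 85 + 28, 85 + 42 and 85 + 56 give Days 99, 113, 127 and 141. These match the schedule exactly.

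**The gap**
- SAE window closes: 85 + 30 = Day 115.
- Days outside it: 141 − 115 = 26 (Days 116 to 141).
- Follow-up length: 141 − 85 = 56 days.
- Share of follow-up: 26 / 56 = 46%. Share of Days 1 to 141: 26 / 141 = 18%.
- Scheduled visits after Day 115: Days 127 and 141, two of the four.

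**Sensitivity to visit windows.** Gap = EoS day − (last-dose day + 30).
- Smallest: 139 − (87 + 30) = 22 days.
- Largest: 143 − (83 + 30) = 30 days.

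**Sensitivity to the EoS date.** SAP Section 7, in describing PK sampling, places the EoS visit at Week 18, whereas both schedules put it at Week 20. With Week 18 (Day 127) the gap would be 127 − 115 = 12 days: smaller, but still present.

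**A serious event on Day 120 in a completer**

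| Instruction | Does it cover the event? |
|---|---|
| 30-day sentence, 9.2.1 | No: Day 120 is after Day 115 |
| Post-discharge duty, 9.2.1 | No: the patient is still in the study |
| Any-SAE alert, 9.2.1 | Yes |
| All AEs recorded, 9.2.1, with AE monitoring on Days 127 and 141 | Yes, as an AE |
| TEAE definitions, Protocol 10.3.4 and SAP 6.2 | Yes, if the event is in the data |

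The answer depends on which sentence the site follows.

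**Start of reporting.** The two rules differ only between consent and first dose (up to 28 days of screening), and only for SAEs unrelated to a study procedure, because the second rule already requires the procedure-related ones. Such events precede the first dose and so are not treatment-emergent.

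**The case against.** The strongest reply is that nothing is shown to be lost. Protocol 9.2.1 defines an SAE as an AE with a serious outcome, so every SAE is also an AE, and all AEs are recorded from consent. A serious event on Day 120 should be entered at the Day 127 visit, and the 24-hour alert duty carries no end date. The SAP works from the eCRF data and has no rule that would drop a late serious event. This stands. A reader might infer that late SAEs will go unrecorded, or that the SAE counts will be incomplete. The documents do not support that: it would follow only if sites let the 30-day sentence override the other instructions.

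It can also be said that the sentence sits between text on patients who have left or completed the study and text on patients discharged from it, so it may be meant as a minimum for those who leave early. Early discontinuers have their EoS activities at discontinuation (Protocol Section 2, footnote b), and for them 30 days may outlast the last visit. This reading is possible, and it is why Day 115 is a completer's figure. But the sentence is not limited to such patients, and a site cannot be expected to infer the limit.

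Nor does the 46% measure lost events. It is a share of follow-up days, and the documents give no SAE rate from which to derive an expected count.

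Finally, the conflict over the start of reporting might be taken to weaken the secondary endpoint. It does not: it concerns sponsor reporting of pre-dose events, which lie outside the treatment-emergent tables.

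**Conclusion.** The collection rule is wrong as written. For completers it closes on Day 115 while visits, AE monitoring and the protocol's TEAE period run to Day 141, a shortfall of 26 days (22 to 30 across the visit windows). What is established is a contradiction between instructions. Its consequence is a risk, not a certainty: late SAEs may be missed or captured differently between sites, and serious and non-serious TEAE tables may rest on different collection periods.

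The figures assume a last dose on Day 85, an EoS visit on Day 141 as in both schedules, and a literal reading of the 30-day sentence. They do not apply to early discontinuers. The conflict over when SAE reporting starts is a separate and lesser matter of sponsor reporting.

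**What to change.** - **Protocol 9.2.1, end of collection.** State that all SAEs, whatever their assessed relationship to treatment, are collected through the patient's last study visit (EoS) or 30 days after the last dose, whichever is later. Tying the end to the patient's own last visit rather than to Day 141 also handles early discontinuers. Keep the post-discharge duty for related events that come to light afterwards.
- **Protocol 9.2.1, start of reporting.** Give one start point and use it in both places. The rule that starts at consent already contains the narrower one.
- **SAP Section 7.** Reconcile the Week 18 timing of the EoS visit with Week 20 in the schedules, so that the end of collection is unambiguous.

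The cost is a protocol wording change and a few more SAE forms. No visit is added, and the SAP's safety tables can stay as planned.

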9.2.1.1. Suspected Unexpected Serious Adverse Reactions

Suspected unexpected serious adverse reactions (SUSARs) are serious events that are not listed in the IB ([PRCL-02 2018](#)) and that the investigator identifies as related to study drug. The sponsor has procedures that will be followed for identifying, recording, and expedited reporting of SUSARs that are consistent with global regulations and the associated detailed guidance.

9.2.2. Complaint Handling

The sponsor collects product complaints on investigational products and drug delivery systems used in clinical studies in order to ensure the safety of study participants, monitor quality, and to facilitate process and product improvements.

Patient will be instructed to contact the investigator as soon as possible if he or she has a complaint or problem with the study drug so that the situation can be assessed.

9.3. Treatment of Overdose

Refer to the IB ([PRCL-02 2018](#)).

9.4. Safety

9.4.1. Electrocardiograms

For each patient, single 12-lead electrocardiograms (ECGs) should be collected according to the Schedule of Activities (Section 2). Patients should be in a supine position for at least 5 minutes prior to recording of an ECG. The screening ECG may be repeated at the discretion of the investigator. Electrocardiograms should be taken prior to other scheduled study procedures taken at similar times, followed by vital signs and then any other study procedures.

Any clinically significant findings from ECGs and that occur after the patient receives the first dose of the study drug should be reported as an AE via EDC.

9.4.2. Vital Signs

For each patient, vital signs (sitting pulse and blood pressure) measurements should be conducted according to the Schedule of Activities (Section 2). Vital signs should be recorded in sitting position just after the ECG (if the ECG is recorded at the same timepoint) and before any other procedures according to the Schedule of Activities (Section 2).

Any clinically significant findings from vital signs measurement that occur after the patient receives the first dose of study drug should be reported as an AE via EDC.

9.4.3. *Laboratory Tests*

For each patient, laboratory tests detailed in [Appendix 2](#) should be conducted according to the Schedule of Activities (Section 2).

With the exception of laboratory test results that may unblind the study, the sponsor or its designee will provide the investigator with the results of laboratory tests analyzed by a central vendor.

Any clinically significant findings from laboratory tests that result in a diagnosis and that occur after the patient receives the first dose of study drug should be reported to the sponsor or its designee as an AE via EDC.

9.4.4. *Physical Examination*

A complete physical examination will be conducted at screening and at Week 4. Physical examination at other scheduled visits must include evaluation of the skin and mucus membranes. Performance of other components of a physical examination at these visits will be at the investigator's discretion. Additionally, a physical examination may be performed at other unscheduled visits at the investigator's discretion, including those visits being made for evaluation of an AE.

9.4.5. *Safety Monitoring*

A study level safety review will be conducted quarterly.

9.4.5.1. *Hepatic Safety Monitoring*

If a study patient experiences elevated ALT ≥ 3 X ULN, ALP ≥ 2 X ULN, or elevated TBL ≥ 2 X ULN, liver testing ([Appendix 4](#)) should be repeated within 3 to 5 days including ALT, AST, ALP, TBL, direct bilirubin, gamma-glutamyl transferase, and creatine kinase to confirm the abnormality and to determine if it is increasing or decreasing. If the abnormality persists or worsens, clinical and laboratory monitoring should be initiated by the investigator and in consultation with the sponsor designated medical monitor. Monitoring of ALT, AST, TBL, and ALP should continue until levels normalize or return to approximate baseline levels.

Hepatic Safety Data Collection

Additional safety data should be collected via the EDC if 1 or more of the following conditions occur:

- elevation of serum ALT to ≥ 5 X ULN on 2 or more consecutive blood tests
- elevated serum TBL to ≥ 2 X ULN (except for cases of known Gilbert's syndrome)
- elevation of serum ALP to ≥ 2 X ULN on 2 or more consecutive blood tests
- patient discontinued from treatment due to a hepatic event or abnormality of liver tests
- hepatic event considered to be a SAE

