8.1. Discontinuation from Study Treatment

Discontinuation due to a hepatic event or liver test abnormality. Patients who are discontinued from using study drug due to a hepatic event or liver test abnormality should have additional hepatic safety data collected via EDC. Discontinuation of the study for abnormal liver tests **should be** considered by the investigator when a patient meets one of the following conditions after consultation with the sponsor designated medical monitor:

- ALT or AST >5X ULN
- ALT or AST >3X ULN along with one or more of the following criteria:
 - sustained for more than 2 weeks or
 - TBL >2X ULN or
 - prothrombin time >1.5X ULN or
 - the appearance of fatigue, nausea, vomiting, right upper-quadrant pain or tenderness, fever, rash, and/or eosinophilia (>5%)
- alkaline phosphatase (ALP) >3X ULN
- ALP >2.5X ULN and TBL >2X ULN
- ALP >2.5X ULN with the appearance of fatigue, nausea, vomiting, right quadrant pain or tenderness, fever, rash, and/or eosinophilia (>5%)

In addition, patients will be discontinued from the study drug in the following circumstances:

- White blood cell count $\geq 1.5X$ ULN or an increase in white blood cells above ULN and $>2X$ ULN from last predose measure
- Neutrophil or total lymphocyte count of $\geq 1.5X$ ULN or an increase in neutrophils or total lymphocytes above ULN and $>2X$ ULN from last predose measure
- Patient received concomitant medication listed in Exclusion Criteria
- Patient's failure to comply with protocol requirements or study-related procedures
- Termination of the study by the sponsor or regulatory authorities

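### An isolated AST rise starts neither the repeat liver panel nor the additional hepatic data collection, although Section 8.1 treats AST and ALT alike

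*Protocol*

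**What the plan says.** **Stopping (Protocol 8.1).** For abnormal liver tests, discontinuation should be "considered by the investigator when a patient meets one of the following conditions after consultation with the sponsor designated medical monitor". The conditions include "ALT or AST >5X ULN" on its own, and "ALT or AST >3X ULN along with one or more of the following criteria", one of which is a rise "sustained for more than 2 weeks". ALT and AST are interchangeable here. Meeting a condition prompts a decision and does not force a stop, so a patient may continue on drug.

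**Repeat testing (Protocol 9.4.5.1).** The rule opens: "If a study patient experiences elevated ALT ≥ 3 X ULN, ALP ≥ 2 X ULN, or elevated TBL ≥ 2 X ULN". Liver tests are then to be repeated within 3 to 5 days. AST is measured in that repeat panel, as is creatine kinase, but an AST value cannot start it. If the abnormality persists or worsens, "clinical and laboratory monitoring should be initiated by the investigator", in consultation with the medical monitor.

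**Additional hepatic data (Protocol 9.4.5.1).** There are five triggers: "elevation of serum ALT to ≥ 5 X ULN on 2 or more consecutive blood tests"; total bilirubin of at least 2x ULN (known Gilbert's excepted); ALP of at least 2x ULN on two consecutive tests; "patient discontinued from treatment due to a hepatic event or abnormality of liver tests"; and a hepatic event that is an SAE. No AST level is listed.

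**Scheduled laboratory tests (Protocol Section 2).** After Day 1 these fall on Days 8, 15, 29, 57 and 85, and then at end of study on Day 141, each with a window of ±2 days. The SAP adds no hepatic rule.

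**The concern.** An AST value high enough to raise the question of stopping drug can leave the protocol's own follow-up rules silent. If the patient stops, additional hepatic data are collected. If the same patient continues, they are not, so for an isolated AST rise the capture depends on the decision and not on the abnormality. No early retest is prescribed to inform that decision either.

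Safety and tolerability is a secondary objective. Section 3.3 describes up to 28 days of dosing in psoriasis patients, and this study doses for 12 weeks, so hepatic information at this duration is new. The protocol does not otherwise treat AST as unimportant: exclusion criterion 16 sets the AST limit for hepatic impairment at 1.5x ULN, tighter than the 2x for ALT. It gives no reason for leaving AST out of the two rules.

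**Working it through.** The plan states no figure to reproduce. The check sets the three rule sets side by side and then measures the retest interval from the schedule.

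**Step 1. Run cases through the rules.** Assumptions: drug continued, no hepatic SAE, every test not named is below its own trigger. Multiples are of ULN.

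| Case | 8.1: consider stopping | 9.4.5.1: repeat in 3–5 days | 9.4.5.1: additional data |
|---|---|---|---|
| ALT 6x | yes | yes | yes, once confirmed |
| AST 6x alone | yes | **no** | **no, even if confirmed** |
| ALT 4x, more than 2 weeks | yes | yes | no |
| AST 4x alone, more than 2 weeks | yes | **no** | no |
| AST 4x with bilirubin 2.1x | yes | yes | yes, through bilirubin (outside known Gilbert's) |

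The ALT and AST rows differ in two places. AST never starts the repeat panel, and AST above 5x never reaches the data list. Where bilirubin rises as well, both steps operate.

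**Step 2. Time to the next required test for an isolated AST rise.** Gap = next scheduled laboratory day minus day first seen. Each visit can move by 2 days, so the range is the gap minus 4 to the gap plus 4.

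| First seen | Next scheduled test | Gap (days) | With windows (days) |
|---|---|---|---|
| Day 8 (Week 1) | Day 15 | 15 − 8 = 7 | 3 to 11 |
| Day 15 (Week 2) | Day 29 | 29 − 15 = 14 | 10 to 18 |
| Day 29 (Week 4) | Day 57 | 57 − 29 = 28 | 24 to 32 |
| Day 57 (Week 8) | Day 85 | 85 − 57 = 28 | 24 to 32 |

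For ALT of at least 3x ULN the corresponding interval is 3 to 5 days throughout.

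**Step 3. Effect on the duration criterion in 8.1.** With scheduled tests only, an AST above 3x ULN first seen on Day 57 can be shown to have lasted more than 14 days only on Day 85, which footnote k of the schedule gives as the last day of dosing.

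**Step 4. The same cases with AST added to both rules.** AST 6x alone: repeat yes, data once confirmed. AST 4x alone for more than 2 weeks: repeat yes, data no. Both rows now match their ALT counterparts.

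**The case against.** The strongest reply is that the stopping list and the data list serve different purposes and need not match, that AST is less specific to the liver than ALT, and that nobody would ignore an AST of 6x ULN. Much of this stands:

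- Scheduled chemistry includes AST, and investigators must document review of each laboratory report (9.2).
- Section 8.1 calls for consultation with the medical monitor, who also follows safety data throughout (9.2.1). A study-level safety review is held quarterly (9.4.5).
- Unscheduled visits with laboratory tests are foreseen (SAP 2.6), and Appendix 4 tests may be obtained for any treatment-emergent hepatic abnormality.
- The intervals in the working are therefore worst cases. They apply only if nobody orders a test between visits.
- The situation is narrow: ALT, ALP and bilirubin all below their triggers, drug continued and no hepatic SAE.

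These safeguards rest on judgement, whereas for ALT the retest and the data trigger are written down. Non-hepatic origin is a fair reason for caution, but the repeat panel already contains creatine kinase to help tell the sources apart.

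A reader might go further and infer that ALT of 3 to 5x ULN with duration, a prolonged prothrombin time or symptoms is left equally uncovered, since those combinations are also absent from the data list. The documents do not support that. ALT of 3x ULN or more already starts the repeat panel, and monitoring follows if the rise persists. Prothrombin time is named in Appendix 2, but footnote j describes the scheduled tests as hematology, chemistry and urinalysis, so a prothrombin result would probably come from a work-up already in hand. New symptoms are recorded as AEs, and eosinophils are in the routine blood count. The protocol does not say what the additional data contain, so no specific loss can be shown for these routes.

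**Conclusion.** The point holds for AST alone, as a cheap improvement. Section 8.1 treats ALT and AST alike, but in 9.4.5.1 an isolated AST rise starts neither the 3-to-5-day repeat panel nor, even when confirmed above 5x ULN, the additional data collection. The practical size is a wait for the next required test of 28 days (24 to 32 with windows) if the rise is first seen at Week 4 or Week 8, instead of 3 to 5 days.

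This assumes ALT below 3x, ALP below 2x and bilirubin below 2x ULN, drug continued, no hepatic SAE, and no discretionary test in between. Section 9.4.5.1 is worded as what should be done, so required here means named in its rules. The documents give no frequency of such rises, and no patient number is claimed.

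It would be wrong to read this as a contradiction between the two sections, or as AST going unmonitored. AST is measured at each scheduled laboratory visit and the discretionary safeguards apply. The primary PASI 75 analysis is not affected.

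**What to change.** Make two edits in Protocol 9.4.5.1:

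1. Add AST of at least 3x ULN to the values that start the repeat liver panel.
2. Widen the first trigger for additional hepatic data to ALT or AST of at least 5x ULN, keeping the requirement for two consecutive tests.

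Leave the Section 8.1 thresholds, the stopping decision, the Gilbert's exception and the other triggers unchanged. Update the matching eCRF trigger.

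The cost is one term in one rule, one changed line in the data list, an occasional repeat panel and a little extra data entry. Some of that will be spent on AST rises that are not of liver origin. The protocol sets no interval for the monitoring that follows a persistent abnormality, so the first edit secures an early confirmation and leaves the later test dates to the investigator and medical monitor, as already happens for ALT.
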